4 INTRODUCTION

This document presents the statistical analysis plan (SAP) for Biogen, Protocol No. 274RP101(formerly NSR-RPGR-01): A Dose Escalation (Phase 1), and Dose Expansion (Phase 2/3) Clinical Trial of Retinal Gene Therapy for X-Linked Retinitis Pigmentosa (XLRP) Using an Adeno-Associated Viral Vector (AAV8) Encoding Retinitis Pigmentosa GTPase Regulator (RPGR) (XIRIUS Study).

This analysis plan is based on the protocol amendment V11 dated 1 Oct 2020; incorporating amendments no. 1, dated 01DEC2016 to amendment no. 11.0, dated 1 Oct 2020.

The SAP provides the description of the final analyses for the generation of the clinical study report.

5 STUDY OBJECTIVES AND ENDPOINTS

5.1 Objective

The objective of the study is to evaluate the safety, tolerability and efficacy of a single subretinal injection of AAV8-RPGR in subjects with XLRP.

5.2 Endpoints

The endpoints in the protocol are listed in a general way. To facilitate statistical analysis plan for each endpoint, more details are provided in this section.

5.2.1 Part I

5.2.1.1 Primary Endpoints

The primary safety endpoints are the incidence of dose-limiting toxicities (DLTs), and treatment-emergent adverse events (TEAEs) over a 24-month period.

5.2.1.2 Secondary and Exploratory Endpoints

- Change from baseline in microperimetry
 - Proportion of study eyes with \geq 7 dB improvement from baseline at \geq 5 out of the 16 central loci in microperimetry at 1, 3, 6, 9, 12, 18 and 24 months, respectively
 - o Proportion of study eyes with ≥7 dB improvement from baseline at ≥5 out of the 68 loci in microperimetry at 1, 3, 6, 9, 12, 18 and 24 months, respectively
 - Change from baseline in Mean Sensitivity of the 16 central loci at 1, 3, 6, 9, 12, 18 and 24 months, respectively
 - Change from baseline in Mean Sensitivity of the 68 central loci at 1, 3, 6, 9, 12, 18 and 24 months, respectively
- Change from baseline in best-corrected visual acuity (BCVA) and Low luminance visual acuity (LLVA)
 - Change from baseline in BCVA at 1, 3, 6, 9, 12, 18 and 24 months, respectively
 - Change from baseline in LLVA at 1, 3, 6, 9, 12, 18 and 24 months, respectively

- Proportion of eyes with a ≥15 letters increase from baseline for BCVA and LLVA at 1, 3, 6, 9, 12, 18 and 24 months, respectively
- Proportion of eyes with a ≥ 10 letters increase from baseline for BCVA and LLVA at 1, 3, 6, 9, 12, 18 and 24 months, respectively
- Proportion of eyes with a ≥5 letters increase from baseline for BCVA and LLVA at 1, 3, 6, 9, 12, 18 and 24 months, respectively
- Proportion of eyes with a ≥15 letters loss from baseline for BCVA and LLVA at 1, 3, 6, 9, 12, 18 and 24 months, respectively
- Proportion of eyes with a ≥10 letters loss from baseline for BCVA and LLVA at 1, 3, 6, 9, 12, 18 and 24 months, respectively
- Proportion of eyes with a ≥5 letters loss from baseline for BCVA and LLVA at 1, 3, 6, 9, 12, 18 and 24 months, respectively
- Proportion of eyes with change from baseline > -5 letters for BCVA and LLVA at 1, 3, 6, 9, 12, 18 and 24 months, respectively
- Change from baseline in spectral domain optical coherence tomography (SD-OCT)
 - Change from baseline in Central Ellipsoid Area at 1, 3, 6, 9, 12, 18 and 24 months, respectively
 - Change from baseline in Central Horizontal Ellipsoid Width at 1, 3, 6, 9, 12, 18 and 24 months, respectively
- Change from baseline in Fundus Autofluorescence at 1, 3, 6, 12, 18 and 24 months
- Change from baseline in other anatomical and functional outcomes at 1, 3, 6, 9, 12, 18 and 24 months, respectively

5.2.2 Part II

5.2.2.1 Primary Efficacy Endpoint

The primary efficacy endpoint is the proportion of study eyes with \geq 7 dB improvement from baseline at \geq 5 of the 16 central loci of the 10-2 grid assessed by Macular Integrity Assessment (MAIA) microperimetry at 12 months.

5.2.2.2 Safety Endpoint

The primary safety endpoint is the incidence of TEAEs over a 12-month period.

5.2.2.3 Secondary Endpoints

- Change from baseline in microperimetry
 - Proportion of study eyes with ≥7 dB improvement from baseline at ≥5 of the 16 central loci in microperimetry at 1, 2, 3, 6 and 9 months, respectively
 - Proportion of study eyes with ≥7 dB improvement from baseline at ≥5 of the 68 loci in microperimetry at 1, 2, 3, 6, 9 and 12 months, respectively
 - Change from baseline in Mean Sensitivity of the 16 central loci at 1, 2, 3, 6, 9 and 12 months, respectively
 - Change from baseline in Mean Sensitivity of the 68 loci at 1, 2, 3, 6, 9, and 12 months, respectively

- Change from baseline in BCVA and LLVA
 - Change from baseline in BCVA and LLVA at 1, 2, 3, 6, 9, and 12 months, respectively
 - Proportion of eyes with a \ge 15 letter increase from baseline at 1, 2, 3, 6, 9, and 12 months, respectively
 - Proportion of eyes with a \ge 10 letter increase from baseline at 1, 2, 3, 6, 9, and 12 months, respectively
 - Proportion of eyes with a \geq 5 letter increase from baseline at 1, 2, 3, 6, 9, and 12 months, respectively
 - o Proportion of eyes with a ≥15 letters loss from baseline for BCVA and LLVA at 1, 2, 3, 6, 9, and 12 months, respectively
 - o Proportion of eyes with a ≥10 letters loss from baseline for BCVA and LLVA at 1, 2, 3, 6, 9, and 12 months, respectively
 - o Proportion of eyes with a ≥5 letters loss from baseline for BCVA and LLVA at 1, 2, 3, 6, 9, and 12 months, respectively
 - Proportion of eyes with change from baseline > -5 letters for BCVA and LLVA at 1, 2, 3, 6, 9, and 12 months, respectively
- Change from baseline in visual field assessed by Octopus 900 at 3, 6 and 12 months, respectively

5.2.2.4 Exploratory Endpoints

6 STUDY DESIGN

6.1 Discussion of Study Design

This is a Phase 1/2/3, first-in-human, multi-center, dose-escalation interventional study of AAV8-RPGR in male subjects with genetically confirmed XLRP. The study will be conducted in 2 parts: Part I is a dose escalation study, Part II is a dose-expansion study, with 2 doses selected from Part I based on safety and efficacy, and a third untreated group to allow for a controlled comparison of efficacy and safety.

Part I will identify the maximum tolerated dose (MTD) using a dose-escalation scheme. Part II will expand 2 doses, allowing for a broader assessment of the safety and efficacy of AAV8-RPGR with a larger sample size, including up to approximately 30 subjects randomized 1:1:1 to a high-dose, a low-dose, and an untreated arm. Part I primarily evaluates safety, defined by incidence of Dose Limiting Toxicities (DLTs) and TEAEs over a 24-month period. Phase II evaluates safety and efficacy, with inclusion of a primary efficacy endpoint, improvement from baseline in microperimetry evaluated at 12 months, and safety and secondary efficacy evaluated at 1, 2, 3, 6, 9, and 12 months post-treatment. An administrative interim analysis may be conducted during follow-up of Part II.

Part I

Part I will use a 3+3 escalation scheme for administration of AAV8-RPGR.

Part I of the study will involve up to 6 dose cohorts, with AAV8-RPGR doses of 5×10^{9} vg (Cohort 1), 1×10^{10} vg (Cohort 2), 5×10^{10} vg (Cohort 3), 1×10^{11} vg (Cohort 4), 2.5×10^{11} vg (Cohort 5), and 5×10^{11} vg (Cohort 6). Each eligible subject will receive AAV8-RPGR in their study eye and be monitored for DLTs.

An Independent Data Monitoring Committee (IDMC) will be used to review safety data before confirming whether escalation to a higher dose level can occur. There is a potential for surgical complications resulting in safety events that meet the criteria for a DLT. In such cases, the IDMC will make the final adjudication as to whether the event is a DLT.

The IDMC will review safety data for each cohort when at least 3 subjects have been dosed at a particular level. However, if 2 subjects within a cohort have a DLT(s), dosing will not proceed to subsequent subjects until safety data are reviewed by the IDMC.

Three to 6 subjects are planned per dose cohort; however, the actual number of subjects enrolled into each cohort will depend on the toxicity observed. If no DLTs are observed in the first 3 subjects treated within a cohort, then escalation to the next dose cohort can proceed. If 1 DLT is reported within a 3-subject cohort, an additional 3 subjects will be added and treated at the same dose level. If there are no further DLTs reported in the additional 3 subjects, then escalation to the next dose cohort can proceed. If ≥ 2 subjects within a cohort (3 or 6 subjects) have a DLT(s), then the MTD will be identified as the previous (lower) dose. Dosing will cease under this protocol and further investigation may occur following a protocol amendment.

Part II

Approximately 30 additional subjects will be randomized in a 1:1:1 allocation ratio to a highdose group $(2.5 \times 10^{11} \text{ vg})$, a low-dose group $(5 \times 10^{10} \text{ vg})$, and an untreated control group.

Study data will be collected for both eyes of each subject. Since treatment requires an invasive surgical procedure under general anaesthesia, the sponsor, investigator and subject will be unmasked to the study procedure (i.e., vitrectomy and sub-retinal injection). However within the treated groups, the sponsor, investigator and subject will be masked to the assigned dose. To further minimise potential bias of the treated and non-treated eye evaluations, all subjective ophthalmic assessments at the Screening/Baseline Visit (Visit 1) and from Month 3 (Visit 6) onwards will be conducted by an assessor who is masked to which eye has received treatment and to which group the subject has been assigned to.

As a note, Version 6 (dated 18MAY18) of the protocol introduced the dose expansion phase of the study, where subjects were to be randomized in 2 groups (i.e., high dose and low dose) in a 2:1 allocation ratio. As of 07 November 2018, 3 subjects were randomized under the 2:1 allocation ratio as per Version 6 (prior to Version 8 finalization).

6.2 Study Treatment

Part I, Dose Escalation: all subjects will undergo vitrectomy and retinal detachment in their study eye and then receive a single, sub-retinal injection of AAV8-RPGR. Subjects will receive an AAV8-RPGR dose of 5×10^{9} vg (Cohort 1), 1×10^{10} vg (Cohort 2), 5×10^{10} vg (Cohort 3), 1×10^{11} vg (Cohort 4), 2.5×10^{11} vg (Cohort 5), or 5×10^{11} vg (Cohort 6).

The layout of the summary table is:

| Cohort 1 | Cohort 2 | Cohort 3 | Cohort 4 | Cohort 5 | Cohort 6 | Cohorta | Dout I |
|----------|----------|----------|----------|-----------|----------|---------|--------|
| 5×10^9 | 1×10^10 | 5×10^10 | 1×10^11 | 2.5×10^11 | 5×10^11 | 3-6 | Total |
| vg | vg | vg | vg | vg | vg | | |

For ocular inflammation-related and visual acuity-related tables, the cohorts of 1-3, and 4-6 will be displayed.

| Cohort 1 | Cohort 2 | Cohort 3 | Cohort 4 | Cohort 5 | Cohort 6 | C 1 4 | C 1 4 | |
|----------|----------|----------|----------|-----------|----------|--------------|----------------|-----------------|
| 5×10^9 | 1×10^10 | 5×10^10 | 1×10^11 | 2.5×10^11 | 5×10^11 | 1-3 | Cohorts 4-6 | Part I Total |
| vg | vg | vg | vg | vg | vg | | | |

Part II, Dose Expansion: subjects will be assigned to one of the following: high-dose $(2.5 \times 10^{11} \text{ vg})$, low-dose $(5 \times 10^{10} \text{ vg})$, or an untreated control arm.

The efficacy summary table will be displayed as:

| High Dose | Low Dose | Dart II Traatad | Port II Untracted |
|--------------|------------|-----------------|-------------------|
| 2.5×10^11 vg | 5×10^10 vg | Fait II fleated | Part II Untreated |

The safety summary table will be displayed as:

| High Dose | Low Dose | | | Part I and II |
|--------------|------------|-----------------|-------------------|----------------------|
| 2.5×10^11 vg | 5×10^10 vg | Part II Treated | Part II Untreated | All Treated Doses |

6.3 Study Schedule

Part I will consist of 11 visits over a 24-month evaluation period. Part II consists of 10 visits over a 12-month period. At the Screening/Baseline Visit, each subject will be assessed for eligibility of both eyes. Only 1 eye will receive treatment (the "study eye"), and the untreated eye will be designated as the "fellow eye". Selection of the "study eye" will be made on clinical grounds and will generally be the worse eye affected.

Subjects will be assessed for safety and efficacy throughout the study as indicated in the Schedule of Study Procedures (refer to the protocol).

Subjects who develop cataracts may undergo cataract surgery if deemed clinically necessary; if surgery is performed, it should be carried out at least 4 weeks before their final visit.

The end of the trial is the date the last subject completes his final-visit assessments (or early termination [ET] assessments in the event of premature discontinuation) or the date of last data collection if the last subject is lost to follow-up.

6.4 Randomization

Part I, the dose-escalation portion of this study, is not randomized.

In Part II, after the study eye is assigned, subjects will be randomized to 1 of 3 groups with a 1:1:1 allocation ratio: (1) treatment with AAV8-RPGR at a high dose $(2.5 \times 10^{11} \text{ vg})$; (2) treatment with AAV8-RPGR at a low dose $(5 \times 10^{10} \text{ vg})$; (3) an untreated control group. Randomization will be generated using a validated system that automates the random assignment to treatment groups. Once a subject is deemed eligible, the investigative site (or authorized designee) will access the system, and the subject will be randomized using a standard randomization procedure.

In Version 6 of the protocol 3 subjects were randomized in 2 groups to high dose and low dose in a 2:1 allocation ratio.

6.5 Masking

Part I of the study is open-label.

Part II is double-masked (sponsor, investigator/site team, and subject will be masked) to the assigned dose, and unmasked with respect to the treatment administration.

In Part II, it is preferable that the same assessor who performed the efficacy endpoint assessments at Screening/Baseline also perform the assessments during the masked period from Month 3 to Month 12. For the immediate post-operative visits, masking of the assessors will not be viable as clinical signs of surgery will be apparent (i.e. redness, swelling). Therefore, unmasked assessors will perform all ophthalmic assessments at Visit 3 (Day 1) and Visit 4 (Day 7). For Visit 6 (Month 3) onwards, masked assessors will be used, as any signs of surgery will have dissipated and it will not be possible clinically to differentiate between those subjects that have not undergone surgery, and those subjects that have undergone surgery and received active treatment. The following assessments will be masked at 3, 6, 9 and 12 months: BCVA, LLVA, microperimetry, contrast sensitivity, and the

Subjects randomized to the untreated control group will not be required to attend the site at Visit 2, 3 or 4. As the key purpose of Visit 2 is surgery, and Visit 3 and 4 are post-operative safety, there is limited utility in control subjects attending. Therefore, to limit the study burden for control subjects, thereby potentially reducing the risk of subject withdrawal at this stage and reducing the possibility of further unmasking due to direct contact and communication with fellow participants, control subjects are not scheduled to attend the clinic for study visits at these times.

In order to minimize bias further, masked assessors will not have access to the subject's medical records, source documentation or eCRF as data entries or notation (such as use of peri-operative corticosteroid) may be sources of unmasking. From Visit 6 (Month 3) onwards, the masked assessor will also read a pre-written statement to each subject, regardless of randomization, reminding them of the masked nature of the study, and to avoid any reference to prior surgery/non-surgery, which eye may have received treatment or to allude to any information that may unmask the assessor as to which group the subject has been assigned to.

Furthermore, it is anticipated that a subset of the subjects participating in the trial will be active on social media. Following appropriate approval by the Independent Ethics Committee (IEC)/Institutional Review Board (IRB), the patient informed consent form will

request that subjects refrain from posting any details of study participation on social media, which may unmask the assessors to the group the subject has been assigned to. This request will be reiterated at subject visits by the investigator and within the pre-written statement.

Subjects randomized to the AAV8-RPGR treatment groups, surgeons, the investigative team and the study sponsor will be masked to which dose of AAV8-RPGR the subject has been assigned to. Unmasked study site personnel will be assigned the responsibility of performing dilution, which will take place in a designated area remote from the investigative team to preserve masking of the treatment arm. Personnel delegated to perform the dilution will not be involved in any other aspect of the study (i.e., consent, safety/efficacy assessments, surgical procedure).

During Part II, an administrative IA may be performed. In the event that an IA is conducted, the study will continue as planned in a masked fashion.

6.6 Sample Size

Due to the nature of the study design of Part I, no formal sample size computation was performed.

In Part II, the primary endpoint is the proportion of study eyes with ≥ 7 dB improvement from baseline at ≥ 5 of the 16 central loci of the 10-2 grid assessed by MAIA microperimetry at 12 months. A sample size of 10 subjects from a treatment group (either high dose or low dose) and 9 subjects from the untreated control group, will provide approximately 87% power, at a right-sided significance level of 0.10 assuming the treatment group has a 50% response rate and the untreated group has a 5% response rate. The power calculation is based on Fisher's Exact-Boschloo test with a Berger-Boos correction of beta = 0.001.

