12.1. Sample Size

Due to the nature of the study design of Part I, no formal sample size computation was performed.

In Part II, the primary endpoint is the proportion of study eyes with ≥ 7 dB improvement from baseline at ≥ 5 of the 16 central loci of the 10-2 grid assessed by MAIA microperimetry at 12 months. A sample size of 10 subjects from a treatment group (either high dose or low dose), and 9 subjects from the untreated control group, will provide approximately 87% power, assuming the treatment group has a 50% response rate and the untreated group has a 5% response rate. The power calculation is based on Fisher Exact-Boschloo test with a Berger-Boos correction of beta = 0.001, at a right-sided significance level of 0.10.

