2 SUMMARY OF CHANGES

Version 1.0 of the XIRIUS Statistical Analysis Plan (dated 21 March 2019) was aligned with the XIRIUS protocol up to version 8.1. Version 2.0 of the SAP was created to align with version 9.0 of the XIRIUS protocol, dated 14 August 2019. These changes are summarized below.

- The primary efficacy endpoint (originally the primary efficacy endpoint is the proportion of study eyes with ≥7 dB improvement from baseline at ≥5 of the 16 central loci in microperimetry at 12 months) was clarified as specifying that the 10-2 grid is used in performing the MAIA microperimetry test.
- Key secondary efficacy endpoints have been eliminated based on protocol assistance received on 18 June 2019 from the European Medicines Agency.

- The outcomes-assessor masking of assessments was clarified for Part II.
- The methodology of the Part II 3-month interim analysis assisted by the Data Monitoring Committee, and the masked and unmasked operational teams are fully described.
- Based on feedback from FDA after submission of version 1.0 of the XIRIUS SAP and a teleconference of 23 May 2019, the primary efficacy analysis population has been changed to the Intent to Treat (ITT) population and not the modified ITT study population, which is now used for sensitivity and supportive analyses only.
- Handling of missing values has been clarified for continuous and categorical endpoints.
- Statistical analyses of the categorical visual acuity endpoints have been clarified for Part II.
- Adaptive-optics optical coherence tomography has been removed from the SAP and protocol.
- Table 2, the Schedule of Study Procedures, has been updated to align with version 9.0 of the XIRIUS protocol.

At that time when protocol V10.0 was amended, SAP was updated accordingly. For SAP version 3.0 it aligns with XIRIUS protocol V11.0, dated 1 Oct 2020. The changes are summarized as below:

- The sample size section was updated due to study drug availability. The power was updated to ensure the study is adequately powered with type I error
- Multiplicity adjustment has been added for testing two doses for the primary endpoint

- Instructions are now provided for missed final visits due to COVID-19, clarifying that observations collected 6 months outside the last visit window will be included in analysis
- Interim analysis description has been updated as it may be implemented, but it is not a requirement
- The definition of the Safety Analysis Set in Part II has been updated

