7.5 Adjustment for Multiplicity

Part I

This is the dose-escalation part of the study to identify the MTD based on the evaluation of the benefit-risk without any formal statistical comparison. Adjustment for multiplicity is, therefore not applicable.

Part II

The primary efficacy endpoint of Part II is defined as the proportion of study eyes with \geq 7 dB improvement from baseline at \geq 5 of the 16 central loci of the 10-2 grid assessed by MAIA microperimetry at 12 months.

At final analysis, the primary endpoint will be tested byHochberg's (Hochberg 1988) step-up method with familywise error rate controlled at right-sided 0.10. The high dose vs. control group, and the low dose vs. control group will be tested respectively. The study will be declared positive if either dose or both doses achieve statistical significance.

Two hypotheses will be tested for primary endpoint:

High dose vs control group:

 $H_0: p_{trt} = p_{untr} \ versus \ H_1: p_{trt} > p_{untr}$

Low dose vs control group:

H₀: $p_{trt} = p_{untr}$ versus H₁: $p_{trt} > p_{untr}$

The algorithm is based on data-driven ordering of hypotheses $H_{(1)}$ and $H_{(2)}$ corresponding to the ordered p-values $P_{(1)} < P_{(2)}$.

Step 1: start with larger p-value $P_{(2)}$. If $P_{(2)} < 0.10$ (one-sided) then reject null hypotheses and claim this test is significant. The remaining hypothesis test is also rejected. Both doses achieve statistical significance. Otherwise if $P_{(2)} \ge 0.10$ this is not significant and proceed to the next test to compare $P_{(1)}$ with 0.05 (one-sided).

Step 2: if $P_{(1)} < 0.05$ (one-sided) then testing stops. The dose associated with $P_{(1)}$ is claimed statistically significant than control group. The dose associated with $P_{(2)}$ is not statistically significant. Or if $P_{(1)} \ge 0.05$ (one-sided) then testing stops and both doses are not statistically significant.

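### The 87% power is for one dose tested alone at one-sided 0.10; under the planned Hochberg rule a lone effective dose has about 72%

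*SAP*

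**What the plan says.** SAP 6.6 bases the Part II power on "A sample size of 10 subjects from a treatment group (either high dose or low dose) and 9 subjects from the untreated control group". It states that this design "will provide approximately 87% power, at a right-sided significance level of 0.10 assuming the treatment group has a 50% response rate"; the rate taken for untreated subjects is 5%. The test is also named: "The power calculation is based on Fisher's Exact-Boschloo test with a Berger-Boos correction of beta = 0.001". Protocol 12.1 gives the same result for the same design: "will provide approximately 87% power, assuming the treatment group has a 50% response rate and the untreated group has a 5% response rate".

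The decision rule is in SAP 7.5 (Adjustment for Multiplicity) and Protocol 12.6.1. Each dose is compared with the untreated group, and the two p-values go through Hochberg's step-up procedure at a familywise one-sided 0.10. The larger p-value is compared with 0.10. If it is below 0.10, both doses are declared. If it is not, the SAP says "this is not significant and proceed to the next test to compare" the smaller p-value with 0.05. The study is positive if at least one dose succeeds.

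Neither sample size section mentions Hochberg or the 0.05 step, and neither document gives power under the procedure. The change list in SAP section 2 records for version 3.0: "The power was updated to ensure the study is adequately powered with type I error". The next item in that list is the addition of the multiplicity adjustment for two doses.

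**The concern.** The power was calculated for one dose against control, with 0.10 as the threshold whatever the other dose does. Under Hochberg a dose has that threshold only when its companion also has p below 0.10. A dose that succeeds alone must reach 0.05. Success of a single dose is an explicit route to a positive study, and the sample size text describes the figure as holding for whichever dose is considered. On that route the 87% does not apply.

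The two doses differ five-fold (2.5×10^11 and 5×10^10 vg), so unequal response is a realistic possibility. A reader who sees one dose fail will weigh that result against an assumed 13% chance of a false negative. If the true chance is about twice that, a failed dose will be taken as stronger evidence of no effect than it is. This matters for a small study that the Version 11 amendment summary says is meant to inform the next pivotal trial.

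**Working it through.** **Inputs.** From SAP 6.6: 10 subjects per dose, 9 untreated; response 50% on an effective dose and 5% untreated; one-sided Boschloo test with Berger-Boos beta 0.001. From SAP 7.5: Hochberg with thresholds 0.10 and 0.05. Two inputs are assumptions. The 10/10/9 split extends the stated 10 versus 9 to three arms. The response rate in the other dose is not given separately, so it is varied from 5% to 50%. No dropout is added, because the plan's calculation has none.

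**Step 1: rejection boundaries.** For each table of *t* responders out of 10 treated and *c* out of 9 untreated, the one-sided Fisher p-value is the test statistic. Its tail probability is maximised over a 99.9% Clopper-Pearson interval for the common rate, and 0.001 is added. The fewest treated responders needed are:

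| Untreated responders *c* | 0 | 1 | 2 | 3 |
|---|---|---|---|---|
| Needed for p < 0.10 | 3 | 4 | 6 | 7 |
| Needed for p < 0.05 | 4 | 5 | 7 | 8 |

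With no untreated responders, 3/10 gives p = 0.063 and 4/10 gives p = 0.027.

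**Step 2: reproduce the stated 87%.** Power = Σ P(C = c) × P(T ≥ boundary for c), with C ~ Bin(9, 0.05) and T ~ Bin(10, 0.5).

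- P(C = 0, 1, 2, 3) = 0.6302, 0.2985, 0.0629, 0.0077.
- P(T ≥ 3, 4, 5, 6, 7, 8) = 0.9453, 0.8281, 0.6230, 0.3770, 0.1719, 0.0547.
- At 0.10: 0.6302×0.9453 + 0.2985×0.8281 + 0.0629×0.3770 + 0.0077×0.1719 = 0.5958 + 0.2472 + 0.0237 + 0.0013 = 0.868.

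This is the plan's 87%, so that figure is the unadjusted single comparison. Terms with *c* of 4 or more add less than 0.0001.

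**Step 3: the same comparison at 0.05.** 0.6302×0.8281 + 0.2985×0.6230 + 0.0629×0.1719 + 0.0077×0.0547 = 0.5219 + 0.1860 + 0.0108 + 0.0004 = 0.719.

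**Step 4: the full Hochberg rule.** All (high, low, untreated) outcomes for 10/10/9 were enumerated with the shared control arm. Both doses are declared if both p-values are below 0.10; otherwise a dose is declared only if its p-value is below 0.05. One dose is at 50% and the control at 5%.

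| Rate in the other dose | Power for the 50% dose | At least one dose declared |
|---|---|---|
| 5% | 72.0% | 72.0% |
| 20% | 75.0% | 75.6% |
| 25% | 76.8% | 78.0% |
| 35% | 80.5% | 83.5% |
| 40% | 82.1% | 86.3% |
| 45% | 83.4% | 88.9% |
| 50% | 84.5% | 91.2% |

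With both doses at 50%, both are declared in 77.7% of trials. As a check, 2 × 84.5% − 77.7% = 91.3%, which agrees with 91.2% within rounding. When the other dose is inactive, the route through its reaching p below 0.10 by chance adds only 72.0 − 71.9 = 0.1 percentage point.

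**The case against.** The 87% is arithmetically right for the conditions that SAP 6.6 lists, and that section does not say the figure is adjusted for two doses. The 72% needs the other dose to respond no better than no treatment, which neither document assumes. The only treated rate given is 50%, and both doses were chosen from Part I on safety and efficacy grounds. If 50% holds for both, power for a given dose is 84.5%, about 2.5 points below the stated value. On the study's own success criterion the chance of at least one win is 91.2%, which is better than 87%. The sample size was fixed by drug expiry, so no different figure would have changed enrolment.

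Much of this stands. The single-comparison figure is correct, 72% is the unfavourable end of the range, and 87% understates the chance of any win when both doses work well. It does not rescue the text. The sample size sections describe one dose against control, not the chance that at least one of two effective doses succeeds. For one dose, the power under the planned rule is below 87% at every rate computed for the other dose, including the most favourable. Read as the chance of any win, 87% is still not reached when the other dose responds at 40% or less.

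**Conclusion.** The concern holds. The stated power belongs to a test that the plan does not use for its decision. Under Hochberg, the power to declare a dose with a 50% response is between 72.0% (other dose at 5%) and 84.5% (other dose at 50%). For a lone effective dose the chance of a miss is 100 − 72.0 = 28.0%, against 100 − 87 = 13% as implied. The power for at least one success ranges from 72.0% to 91.2% over the same scenarios.

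These values rest on the plan's rates of 50% and 5%, a 10/10/9 split, complete data, and the Boschloo test with Berger-Boos correction as specified. Neither the decision rule nor the type I error control is in question.

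**What to change.** In SAP 6.6 and Protocol 12.1, state the power under the Hochberg procedure. Suggested wording: *With 10, 10 and 9 subjects on high dose, low dose and no treatment, and response rates of 50% on an effective dose and 5% untreated, the power to declare a given effective dose under the Hochberg procedure is about 72% if the other dose responds at the untreated rate and about 84% if both doses respond at 50%. If both respond at 50%, the power to declare at least one dose is about 91%, and to declare both about 78%.*

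Remove the statement that 87% applies to either dose. If the figure is kept for reference, label it as one unadjusted comparison at one-sided 0.10. The claim of adequate power in the SAP change list should then refer to the restated figures.

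The cost is wording only: no more subjects, and no change to the test, the alpha or the decision rule. The power quoted for a single dose becomes less favourable.
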